8.3.5. Uroflowmetry

- Summary statistics for uroflowmetry parameters (free Q_{max}, free Q_{ave}, voided volume, and voiding time) at the time of enrollment and Week 8 of treatment will be calculated.
- Summary statistics for change from baseline in the observed value of uroflowmetry parameters at Week 8 of treatment will be calculated.
- For amounts of changes in measured values of uroflowmetry parameters at Week 8 from values immediately before the start of treatment to each evaluation time point, student's t-test will be conducted using the placebo group as the control.

8.3.6. Residual Urine Volume

- Summary statistics at the time of enrollment in the observation period, at the time of enrollment in the treatment period, and Week 8 of treatment will be calculated.
- Summary statistics for change from baseline in the observed value at Week 8 of treatment will be calculated.
- For amounts of changes in measured values at Week 8 from values immediately before the start of treatment to each evaluation time point, student's t-test will be conducted using the placebo group as the control.

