Urinary flow test			X				X		X
Measurement of residual urine volume by ultrasonography	X 		X				X		X
Concomitant drugs and therapies 									X
Evaluation of adverse events 									X

1. Acquisition of consent: Consent is obtained within 28 days before the enrollment in the observation period.

2. Laboratory test: Hematological tests, serum chemistry and urinalysis are performed.

3. Pregnancy test: Required. When at least 1 year has passed after menopause or when the possibility of pregnancy is medically denied, the test is not necessary. The pregnancy test (serum or urine) before the enrollment must be negative.

4. Concomitant drugs/therapies, evaluation of adverse events: Investigated from the acquisition of consent to the completion of the follow-up observation period.
5. Acceptable range of observation period: Observation period is 3 weeks in principle, but up to 4 weeks is permitted.
6. Acceptable range of timings of visits in treatment period: Week 4 and Week 8 visits  $\pm$  3 days from the scheduled dates are permitted.
7. Follow-up observation: Observation is performed 2 to 4 weeks after the completion of Week 8 of the treatment period. When the treatment is discontinued, it is performed 2 to 4 weeks after the last administration of the study drugs.
8. In cases of discontinuation: Specified observation and tests are performed as much as possible.
9. When the specified observation and tests were performed within 14 days before the enrollment, even if it was before the consent, the results can be used as the data at the time of the enrollment in the observation period.

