#### 1.4.2 Drugs with Similar Mechanism of Action to That of TAS-303

As drugs with the same mechanism of action as that of TAS-303, which is an inhibitory action on NA reuptake, atomoxetine hydrochloride and amezinium metilsulfate are on the market. The main adverse reactions to atomoxetine hydrochloride are shown in [Table 1.4.2-1](#) and the main adverse reactions to amezinium metilsulfate in [Table 1.4.2-2](#). As serious adverse reactions to atomoxetine hydrochloride, hepatic function disorder, jaundice, hepatic failure (incidence unknown) and anaphylaxis (incidence unknown) have been reported.

Table 1.4.2-1 Main Adverse Reactions to Atomoxetine Hydrochloride

Category of adverse reactions	5% or higher	1% or higher and less than 5 %
Gastrointestinal	Nausea, decreased appetite, abdominal pain, vomiting, constipation, thirst	Diarrhoea, dyspepsia, dry mouth
Neuropsychiatric	Headache, somnolence, dizziness	Dizziness postural, sleep disorder, irritability, dysphoria, insomnia
Hypersensitivity	-	Pruritus
Cardiovascular	Palpitations	Tachycardia, blood pressure increased, heart rate increased
Dermatological	-	Hyperhidrosis
Urogenital	-	Dysuria, erectile dysfunction
Other	Weight decreased	Chest pain, asthenia, fatigue, hot flush, chills, dysgeusia

Table 1.4.2-2 Main Adverse Reactions to Amezinium Metilsulfate

Category of adverse reactions	0.1% or higher and less than 5 %
Gastrointestinal	Queasy/vomiting, abdominal pain
Neuropsychiatric	Giddiness, dizziness on standing up, headache, heaviness of head, feels poorly
Cardiovascular	Palpitations, tachycardia, blood pressure fluctuation, arrhythmia (eg., extrasystoles, atrial fibrillation), feeling of hot flushes, feeling of hot flash
Hepatic	Hepatic function abnormal including AST increased and ALT increased
Other	Urination impaired

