### **2.3.2.2 Safety**

- (1) Status of onset of adverse events and adverse reactions
- (2) Vital signs (blood pressure, pulse rate, body temperature), 12-lead electrocardiogram, laboratory tests
- (3) Urinary flow test parameters
 

Maximum urinary flow rate: Free  $Q_{max}$ , average urinary flow rate: free  $Q_{ave}$ , voided volume, time of voiding (at the time of enrollment in treatment period, Week 8)
- (4) Residual urine volume (at the time of enrollment in observation period, at the time of enrollment in treatment period, Week 8)
- (5) Mean number of urinations per 24 hours in urination record (at the time of enrollment in treatment period, Week 4, Week 8)

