11.2. Handling of Dropouts or Missing Data

Handling of missing values in efficacy endpoints will be specified for each analysis.

Missing values in safety endpoints will not be imputed. The proportion, including that of patients with adverse events, will be calculated using the analysis population as the denominator for the observation period and using the number of patients who have taken study drugs for the treatment period at least once among those in the analysis population as the denominator for the treatment period.

Analyses will include all measured data, except for abnormal laboratory test values with obvious reasons, such as the effect of hemolysis during blood collection. If abnormal values are excluded from the analysis, they will be specified and reasons for exclusion will be stated.

In the case of any post hoc exploratory analysis, the procedure for handling of missing data will be determined appropriately for each item to be analyzed according to the method of analysis and characteristics of items to be evaluated.

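### No analysis specified in the SAP uses residual urine and urinary flow values taken at discontinuation, although they are an early stopper's only post-randomisation voiding measurements

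*SAP*

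**What the plan says.** The schedule (protocol synopsis Table 2, repeated as Table 5-2) has rows for "Urinary flow test" and "Measurement of residual urine volume by ultrasonography". After randomisation both are marked at Week 8 and at discontinuation, but not at Week 4 or follow-up. Note 8 to the table qualifies the discontinuation visit: "In cases of discontinuation: Specified observation and tests are performed as much as possible".

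Protocol 2.3.2.2 fixes the time points of the safety endpoint: "Residual urine volume (at the time of enrollment in observation period, at the time of enrollment in treatment period, Week 8". Its entry for urinary flow names enrolment in the treatment period and Week 8.

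The SAP follows that list. Section 8.3.6 says of residual urine: "Summary statistics for change from baseline in the observed value at Week 8 of treatment will be calculated". Section 8.3.5 says of urinary flow: "Summary statistics for change from baseline in the observed value of uroflowmetry parameters at Week 8 of treatment will be calculated". The t-tests against placebo in both sections are also tied to Week 8. SAP 11.2 adds: "Missing values in safety endpoints will not be imputed".

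Protocol 1.4.2 describes two marketed drugs as sharing the noradrenaline reuptake mechanism. It lists dysuria for atomoxetine (1% to under 5%) and "Urination impaired" for amezinium (0.1% to under 5%).

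**The concern.** For a patient who stops before Week 8, the discontinuation visit gives the only flow and residual urine values after randomisation. If the SAP is followed as written, those values enter no summary, change from baseline or test.

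The Week 8 comparison is then restricted to patients still being assessed at Week 8. If some patients stop because voiding has become difficult, which protocol 4.3(1) allows as an adverse event, the missing Week 8 values are related to the harm being measured. The comparison could then understate it. SAP 6.2.2.1 includes the maximum among its summary statistics, and the largest rise in residual urine in an arm could be one that the Week 8 table omits.

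The patient has undergone the test, so the value is lost to the specified analyses only because no rule brings it in.

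**Working it through.** **Step 1. Set the passages side by side.**

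| Source | Post-randomisation points for flow and residual urine |
|---|---|
| Synopsis Table 2 | Week 8; discontinuation |
| Protocol 2.3.2.2 | Week 8 |
| SAP 8.3.5 (flow) | Week 8 |
| SAP 8.3.6 (residual urine) | Week 8 |
| SAP 11.2 | no imputation of safety values |

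The columns of Table 5-2 are broken in the extracted text, so the reading rests on the synopsis table. There the laboratory row has marks in both the follow-up and the discontinuation columns, while the flow and residual urine rows skip follow-up. No SAP section maps a discontinuation value to Week 8, defines a last or worst value on treatment, or specifies a category table or listing for these two tests.

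**Step 2. Reproduce the plan's sample size, to fix the arm size and withdrawal rate.** SAP 2.2.2 gives a difference of 20, SD 35, two-sided 2.5% per test, power 90% and withdrawal of about 5%.

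- Normal approximation: n = 2 × (2.241 + 1.282)² × 35² / 20² = 76.0, rounded up to 77. Then 77 / 0.95 = 81.1, rounded up to 82 per arm (246 in total).
- Noncentral t: n = 78. Then 78 / 0.95 = 82.1, rounded up to 83 per arm (249 in total).

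The plan's 83 per group and approximately 250 are reproduced.

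**Step 3. Count the patients without a Week 8 value.** 0.05 × 83 = 4.15 per arm and 0.05 × 250 = 12.5 in all. This is withdrawal for any reason.

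**Step 4. Illustrate the effect on the mean.** The documents give no distribution for residual urine, so these inputs are assumed: k patients in one active arm stop with a rise of R mL, and everyone else has a mean change of 0. The Week 8 mean change is then 0 by construction. With the discontinuation values it is k × R / 83.

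| k | R = 50 mL | R = 100 mL | R = 200 mL |
|---|---|---|---|
| 1 | 0.6 | 1.2 | 2.4 |
| 2 | 1.2 | 2.4 | 4.8 |
| 4 | 2.4 | 4.8 | 9.6 |

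**Step 5. Illustrate the effect on the t-test.** The assumptions are SD 20 to 40 mL, 79 completers plus 4 withdrawals per arm, rises of 100 to 150 mL, and 20,000 replicates. The chance of p < 0.05 is about 5% among completers. With the discontinuation values it is about 6% to 8% for k = 2 and about 10% to 26% for k = 4.

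**Step 6. Illustrate the effect on the tail.** Suppose four patients in an arm stop with residual urine of 100 mL or more and no completer reaches that volume. The Week 8 table shows 0/79. With the discontinuation values the share is 4/83 = 4.8% (exact 95% CI 1.3% to 11.9%). The reported maximum omits all four.

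**The case against.** The strongest objection is that the harm is still reported. A patient who stops under protocol 4.3(1) has an adverse event by definition, and protocol 5.1.4 requires clinically significant abnormal findings to be recorded as adverse events. SAP 8.3.1 reports adverse events by arm, severity and time of onset, with a listing. SAP 8.2.2 tabulates the reason for and timing of discontinuation. This stands. A reader might infer that patients who stop with impaired voiding disappear from the safety analysis; they do not. They leave only the measured voiding analysis, although an adverse event term gives no volume or flow rate.

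Other parts of the objection also stand:

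- **Absence from all outputs is not established.** SAP 12 says that the full list of analyses is in a Table and Figure Plan, which is not available. Protocol 13.1.3.3 summarises these tests at every evaluation time point without naming Week 8. That wording does not by itself bring the values in, because protocol 2.3.2.2 and the SAP name the points.
- **Some values will not exist.** Discontinuation tests depend on feasibility, and withdrawal of consent is a reason for stopping (protocol 4.3(2)).
- **Losses mainly from the active arms are not documented.** The idea is plausible from the drug class, but the documents give no number or arm for such patients.
- **The illustration is favourable by construction.** It places all the harm in patients who stop. A general drug effect on voiding would also show in the roughly 79 completers per arm. The k = 4 case needs every withdrawal in one arm to be a marked rise in residual urine.

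A reader might also extend the point to blood pressure, pulse and laboratory tests. That does not follow: the schedule also measures these at Week 4 and follow-up, and SAP 8.3.2 and 8.3.4 summarise them at every evaluation time point.

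**Conclusion.** The point holds in a limited form. Any discontinuation value of residual urine or urinary flow is an early stopper's only post-randomisation measurement, and no analysis specified in the SAP uses it. The SAP does not depart from the protocol here; the protocol's endpoint list has the same gap.

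About 4 of 83 patients per arm would have no Week 8 value at the planned withdrawal rate. The share of them who stop for a voiding problem is unknown and could be none. A reader might infer a demonstrated bias in the mean and t-test, but the documents do not support that. Understatement is possible only if patients stop for this reason. Even under the assumed rises, the mean moves by 0.6 to 9.6 mL, and with two such patients the t-test hardly changes. The real loss is in the extremes: the maximum and the number of patients with a large residual volume. It is worth correcting because the correction is cheap and uses values that the schedule already asks for.

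**What to change.** Keep the Week 8 analyses. In SAP 8.3.5 and 8.3.6 add:

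1. A row called *last treatment-period value*, defined as the Week 8 value or, if there is none, the discontinuation-visit value. Give summary statistics and change from baseline by arm for residual urine, free Qmax, free Qave, voided volume and voiding time.
2. A by-arm listing of all discontinuation values with days since last dose.
3. For residual urine, a by-arm count of patients at 100 mL or more. Protocol 4.2.1 and 4.2.2 already use this volume for eligibility; here it would serve only as a descriptive category, with no bearing on patient management.

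If the key code has already been broken, record these in the change log as planned afterwards, as SAP 10 requires. If the Table and Figure Plan already contains the listing, refer to it.

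The cost is a few sentences, one extra row per table and one listing. No new measurement or imputation is needed, and the sample size does not change. The drawback is that the new row mixes different lengths of exposure and includes some measurements made off drug. Keeping the Week 8 row beside it and listing days since last dose lets the reader see this.

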8.3.7. Mean Frequency of Micturition per 24 Hours

- Summary statistics at the time of enrollment and Weeks 4 and 8 of treatment will be calculated.
- Summary statistics for change from baseline in the observed value at Weeks 4 and 8 of treatment will be calculated.
- For amounts of changes in measured values at Weeks 4 and 8 from values immediately before the start of treatment to each evaluation time point, student's t-test will be conducted using the placebo group as the control.
- Above analyses will be performed by status of urinary incontinence (SUI, MUI).

9. OTHER ANALYSES

9.1. Analysis Populations

The proportion of each analysis population and reasons for exclusion will be tabulated by treatment group. Patients excluded from analysis populations will be listed along with reasons.

9.2. Deviation

The presence or absence of deviations and deviation items will be tabulated by treatment group. A detailed list of patients with deviations will be presented.

10. REVIEW AND REVISION OF STATISTICAL ANALYSIS PLAN

The statistical analysis plan will be finalized before key code breaking.

If the statistical analysis plan is revised, the change log of Statistical Analysis Plan/Table and Figure Plan should be prepared to record the changed content and the reason. Analyses newly planned after key code breaking should be distinguished from those planned beforehand and recorded in the change log.

11. STATISTICAL ISSUES

Explanations on ICH-E3 Guidelines¹⁾ and other statistical issues are summarized below.

11.1. Adjustments for Covariates

Adjustments for covariates will be performed using MMRM. Details of covariates will be specified separately.

11.2. Handling of Dropouts or Missing Data

Handling of missing values in efficacy endpoints will be specified for each analysis.

Missing values in safety endpoints will not be imputed. The proportion, including that of patients with adverse events, will be calculated using the analysis population as the denominator for the observation period and using the number of patients who have taken study drugs for the treatment period at least once among those in the analysis population as the denominator for the treatment period.

Analyses will include all measured data, except for abnormal laboratory test values with obvious reasons, such as the effect of hemolysis during blood collection. If abnormal values are excluded from the analysis, they will be specified and reasons for exclusion will be stated.

In the case of any post hoc exploratory analysis, the procedure for handling of missing data will be determined appropriately for each item to be analyzed according to the method of analysis and characteristics of items to be evaluated.

11.3. Interim Analyses and Data Monitoring

Interim analyses will not be conducted in this study.

11.4. Multicenter Studies

This study is a multicenter study.

11.5. Multiple Comparisons/Multiplicity

In the analysis of the primary objective, the significance level for each comparison will be adjusted by the Hochberg's method, considering multiplicity.

11.6. Use of an "Efficacy Subset" of Patients

Although not planned in this study, additional analyses may be performed as necessary.

11.7. Active-Control Studies Intended to Show Equivalence

Not applicable for this study

11.8. Examination of Subgroups

In this study, subgroup analyses by allocation adjustment factors are planned for some analyses. Additional analyses will be performed as necessary.

12. PREPARATION OF TABLE AND FIGURE PLAN

The statistical analysis plan only specifies major analysis items. All analysis items to be performed will be presented separately in the Table and Figure Plan.

